07 DEC 2018	Amendment 1	
The following change was made:
 
3.2 Study Population (page 14, 3.2 paragraph 2)
 
All patients will be followed during routine clinical practice and will not be burdened with additional site visits or medical procedures, besides their routine treatment. Inclusion into the study is independent from prescription of Juluca. and is capped at a maximum of 5 patients per month and 30 patients per site in total.
 
Rationale
 
This limit was set to prevent too many patients being contributed from a limited number of sites, thus ensuring the multicenter character of the study. As 17 out of 26 possible sites have already enrolled patients, this is no longer an issue and removing this limit will both ensure a timely recruitment and allow the study to be a true account of the real world use of Juluca.

15.06.2020	Amendment 2	
The following changes were made:
 
Second sponsor signatory and study principal investigator [name] [name] is no longer associated with the study. The role of study principal

		investigator is now being fulfilled by Dr. med. Dr. phil. [name].
--	--	---

Description: JUNGLE
Unique Identifier /eTrack ID: 208982

SPONSOR SIGNATORY

Date

.....
[name]
Head, Global Medical Sciences, ViiV Healthcare

STUDY PRINCIPAL INVESTIGATOR SIGNATORY

Date

.....
Dr. med. Dr. phil. [name]
MVZ Stachus, Germany

Description: JUNGLE
Unique Identifier / eTrack ID: 208982

Investigator Protocol Agreement Page

- I confirm agreement to conduct the study in compliance with the protocol.
- I acknowledge that I am responsible for overall study conduct. I agree to personally conduct or supervise the described clinical study.
- I agree to ensure that all associates, colleagues and employees assisting in the conduct of the study are informed about their obligations. Mechanisms are in place to ensure that site staff receives the appropriate information throughout the study.

Investigator Name:

Investigator Signature

Date (DD-MMM-YYYY)

PROTOCOL SYNOPSIS

Unique Identifier/eTrack	208982
Abbreviated Title	JUNGLE
ViiV Product	Dolutegravir/Rilpivirine; JULUCA
Rationale	Gather real-world data on Juluca use in routine clinical care in Germany, to supplement clinical trial data to further improve / optimize patient care in PLHIV in Germany
Objectives (Primary, Secondary)	
Primary objective:
 
 • Evaluate sustainability of antiretroviral suppression in suppressed patients using Juluca in routine clinical care in Germany to evaluate antiretroviral efficacy of the novel 2-Drug Regimen (2DR) of Juluca 
Secondary objectives:
 
 • Gain an understanding of the major relevant patient populations for Juluca in Germany, in terms of patient characteristics and history • Describe real-life efficacy profile of Juluca • Describe real-life tolerability profile of Juluca as measured by discontinuation rates due to adverse drug reactions (ADRs) and overall number of serious adverse events (SAE) • Analyze the development of viral resistance by evaluating available resistance data in case of virologic failure • Describe impact on lipid metabolism • Evaluate medical need for a substance and/or class sparing treatment regimen by assessing the reason for switching to Juluca • Describe patients' treatment satisfaction and symptom distress based on validated questionnaires • Evaluate number of monitoring measures and referrals to other specialists
Study Design	Prospective, non-interventional, single-arm, multi-center study of patients with a clinical indication for HIV-1 therapy in routine clinical care with an observational period of 3 years
Study Population and Sampling Methods	N=250 HIV-1 positive patients are aimed to be included into this study. Subjects must be on stable ART for at least 6 months prior to the inclusion into this study. Patients' eligibility is based on the local SmPC of Juluca. Any subject with contraindications for Juluca are ineligible for study participation.

	
Inclusion criteria:
 
 • ≥ 18 years of age • Documented HIV-1 infection • Virologically suppressed (HIV-1 RNA < 50 c/mL for at least 6 months) • Prescription for Juluca was issued independently from entering this study • Ability to understand informed consent form and other relevant study documents 
Exclusion criteria:
 
 • Any contraindication according to Juluca SmPC • Documented viral load > 50 c/ml at any timepoint within 6 months prior to inclusion into this study • History of treatment failure • Known or suspected substitutions associated with resistance to any NNRTI or INSTI • Any antiretroviral therapy for the treatment of HIV-1 in addition to Juluca • HBV-coinfection • Current participation in the ongoing non-interventional study TRIUMPH (study number: 202033) or any interventional clinical trial irrespective of indication • Previous participation in clinical trials involving Juluca 
Investigators may enroll eligible subjects according to their availability and accessibility. The sample is deliberately non-stratified to reduce limitations on recruitment. This non-probabilistic convenience sampling may not ensure for the sample group to be a true representative of the population without sampling error.

Data Source	
 • Data collected during routine clinical care will be documented as study visits. This may include data from hospital records, clinical charts, electronic patient records or laboratory notes • Once a year and additionally at first follow-up visit, patients will be asked to complete the HIV Symptom Distress Module and the HIV treatment satisfaction questionnaire on a voluntary basis • At each visit, patients will be prompted to give an estimate of their level of adherence in a single-item question

Data Analysis Methods	
Descriptive statistics will be used to analyze all primary and secondary objectives for both total patient population and for pre-defined subgroups. The used questionnaires will be analyzed according to their respective validated scoring instructions.
 
Detailed methodology for summary and statistical analysis of data collected in this study as well as data sets will be specified in a Statistical Analysis Plan (SAP) prior to database lock.

Sample Size and Power	
Sample size was calculated based on the assumption of an antiviral efficacy of 90% (defined as VL <50 c/ml) and a max. study dropout rate of 30% over a period of 3 years. To reach a level of confidence of 95% with a target width of 0.1 (10%), a minimum of N=158 subjects are needed at the end of the study. When max. drop-out rate is included, a minimum number of N=226 subjects are needed. Therefore, the recruitment goal is N=250.

Limitations	
This is a non-interventional, single-arm study aimed at gathering real-world data on the use of Juluca in routine clinical care in Germany. As such there are a number of limitations. The sample is deliberately non-stratified to reduce limitations on recruitment. And with convenience sampling, the population may also be subject to selection bias. Thus, this approach may result in some characteristics being over or under-represented within the sample and limited diversity in terms of demographics and introduction of confounding factors.
 
However, real world data may provide valuable evidence for a patient population that is broader than that of controlled clinical trials, thus enhancing the generalizability and transferability of findings despite large random variations due to a heterogenic patient population.

TABLE OF CONTENTS

1	INTRODUCTION/BACKGROUND.....	12
2	OBJECTIVES	14
2.1	Primary.....	14
2.2	Secondary.....	14
3	RESEARCH METHODOLOGY.....	15
3.1	Study Design	15
3.2	Study Population	15
3.2.1	Eligibility Criteria	15
3.2.2	Sampling.....	16
3.3	Data Source / Data Collection.....	17
3.3.1	Data documented by study sites.....	17
3.3.2	Patient reported data sources (non-mandatory).....	17
3.3.3	Data collection.....	17
3.4	Endpoints	18
3.4.1	Primary Endpoint.....	18
3.4.2	Secondary Endpoints [analyzed at year 1, 2, 3 unless otherwise stated]	18
3.5	Sample Size / Power Calculations	19
3.6	Hypotheses.....	19
4	DATA ANALYSIS CONSIDERATIONS	20
5	LIMITATIONS	21
6	STUDY CONDUCT, MANAGEMENT & ETHICS	22
6.1	Ethics Committee/IRB Approval.....	22
6.2	Informed Consent	22
6.2.1	Written informed consent.....	22
6.2.2	Withdrawal of consent.....	22
6.2.3	Withdrawal from the study by investigator or sponsor.....	22
6.3	Data Protection	23
6.4	Personal Identifiable Information (PII)	23
6.5	Adverse Event (AE), Pregnancy Exposure, and Incident Reporting	24
6.5.1	Definition of adverse events.....	24
6.5.2	Data collected for adverse events	24
6.5.3	Definition of seriousness.....	25

1 INTRODUCTION/BACKGROUND

2-Drug Regimens (2DR) have been investigated for a long time within the HIV community to address special needs of their patients with regard to resistance and / or tolerability issues of existing antiretrovirals [1]. These approaches have been driven by the need to find appropriate treatment regimens for patients with limited therapy options. However, several approaches have shown very promising results in naïve and in pre-treated patients [1, 2, 3].

The SWORD-1 & -2 studies are the first globally conducted registrational trials investigating antiretroviral treatment regimens consisting of 2 substances. The trial data has shown the high potential of the novel 2DR DTG+RPV in stably suppressed HIV-1 patients. The efficacy was non-inferior to the control arm in which patients continued their current ART until the measurement of the primary study endpoint at 48 weeks with 95% of patients below 50 HIV RNA copies/ml. The safety and tolerability profile was good, resulting in only 3% study discontinuations due to drug-related adverse events until week 48 in the DTG+RPV arm [1]. Patient related outcomes revealed a high rate of treatment satisfaction, which was, although very high at baseline in both arms, significantly increased in the DTG+RPV arm. A significant increase compared to the control arm, has been shown in the symptom distress scale, underlining the good tolerability of this regimen [2]. As of November, 21st 2017, Juluca, the first 2-Drug Regimen consisting of DTG and RPV, is licensed in the US for the maintenance treatment of HIV-1 infection in adults who are virologic suppressed (HIV-1 RNA <50 c/ml) on a stable antiretroviral regimen for at least 6 months with no history of treatment failure or known or suspected substitutions associated with resistance to the individual components of Juluca [3].

In 2016, more than 88.000 patients in Germany were living with HIV, of which 75.700 were aware of their diagnosis and 64.900 were under ART [4]. Based on the current German-Austrian HIV Treatment Guidelines, HIV therapy should be initiated regardless of the CD4 cell count with either Integrase-Inhibitors (INSTI), the NNRTI Rilpivirine or Protease-Inhibitors (PI) (Darunavir or Atazanavir) in combination with a background regimen based on two NRTIs. Monotherapy is generally not recommended as initial therapy. Class- or substance-sparing combinations are mentioned, especially the combination of boosted Lopinavir with 3TC, however, it is not recommended as first-line therapy due to limited clinical experience. The recommendations for treatment switches rely on individual patient characteristics, such as resistance and intolerance, without providing clear guidance. [5]. However, based on the Positive Perspectives study, which is a survey with patients from 9 countries with over 1000 participants answering a questionnaire about psychological aspects of living with HIV, the dialogue between HCP and patients, and patients' treatment satisfaction, there are concerns about ART-related long-term toxicities in patients, favoring substance- or class-sparing treatment options [6]. This possibility to use class-/substance-sparing treatment strategies has been implemented very recently in the EACS guidelines, describing DTG+RPV as a treatment option in suppressed patients [7]. Furthermore,

the current DHHS guidelines mention DTG+RPV as a reasonable option when the use of NRTI is not desirable [8].

Regardless of the current treatment status of a patient, antiretroviral therapy must be taken lifelong to ensure suppression of viral replication, which is the overarching treatment goal and reduces the risk of HIV-associated complications, such as immunosuppression and the occurrence of opportunistic infections, as well as a chronic inflammation, which can result in a higher risk for cardiovascular events. Although antiviral therapies have been improved over the last decades in terms of efficacy and tolerability, most therapies require 3 or more drugs to achieve the overarching therapy goal of viral suppression. This is accompanied with the risk of drug-drug interactions, especially in the case when pharmacologic boosters are required to improve PK-profiles of distinct substances, such as protease-inhibitors and the integrase-inhibitor Elvitegravir [5]. Providing therapies with only two drugs, as in Juluca (DTG / RPV), addresses this obstacle in therapy, with a complete antiretroviral regimen with just 2 active substances. This might be beneficial in terms of pharmacology, especially taking into account that over 50% of all patients living with HIV in Germany are 45 years of age and older. Recent publications have shown, that about 20% of the general population, irrespective of their HIV status, have an intake of at least 2 non-ART drugs in that age category of 50 years or older [9]. Furthermore, it might be beneficial in terms of reducing the overall substance burden during a patients' life, when considered, that patients who have been infected and started their therapy between 2008 and 2010, have a life-expectancy of 78 years, meaning almost six decades of antiviral therapy [10].

Non-interventional studies (NIS) provide insights into the medication use in routine clinical care and generate real-world evidence for the used ART in terms of efficacy and tolerability, which can supplement data from randomized clinical trials.

ViiV Healthcare (VH) Germany is currently sponsoring two NIS, DOL-ART and TRIUMPH, observing patients taking either DTG or Triumeq in routine clinical care. Data generated in both studies are published regularly twice a year on national and international conferences to inform HCPs about the real-world profile of DTG when it is used in routine clinical care in Germany.

Likewise, a prospective multicenter NIS for Juluca will assess the drug profile of the first 2DR in a routine clinical setting in Germany.

2 OBJECTIVES

2.1 Primary

Evaluate sustainability of antiretroviral suppression in suppressed patients using Juluca in routine clinical care in Germany to evaluate antiretroviral efficacy of the novel 2-Drug Regimen (2DR) of Juluca

2.2 Secondary

- Gain an understanding of the major relevant patient populations for Juluca in Germany, in terms of patient characteristics and history
- Describe real-life efficacy profile of Juluca
- Describe real-life tolerability profile of Juluca as measured by discontinuation rates due to adverse drug reactions (ADRs) and overall number of serious adverse events (SAE)
- Analyze the development of viral resistance by evaluating available resistance data in case of virologic failure
- Describe impact on lipid metabolism
- Evaluate medical need for a substance and/or class sparing treatment regimen by assessing the reason for switching to Juluca
- Describe patients' treatment satisfaction and symptom distress based on validated questionnaires
- Evaluate number of monitoring measures and referrals to other specialists

3 RESEARCH METHODOLOGY

3.1 Study Design

This is a non-interventional, single-arm, prospective, multi-center study aimed at generating real-world data for the use of Juluca in HIV-1-positive patients as indicated by the local SmPC in routine clinical care in Germany to supplement data obtained from controlled clinical trials.

Eligible subjects will be followed up for approximately 3 years collecting information that can be obtained in routine clinical care.

For a detailed schematic of study visits please refer to Appendix 1.

3.2 Study Population

Aim is the recruitment of 250 treatment-experienced and virologically suppressed patients as indicated by the local SmPC of Juluca at the discretion of the treating physician. Recruitment is expected to be concluded within an approximate timeframe of 6 months. If 250 patients cannot be recruited within this timeframe, recruitment period may be extended until a minimum number of 180 patients is reached.

All patients will be followed during routine clinical practice and will not be burdened with additional site visits or medical procedures, besides their routine treatment. Inclusion into the study is independent from prescription of Juluca.

3.2.1 Eligibility Criteria

3.2.1.1 Inclusion Criteria

- ≥ 18 years of age
- Documented HIV-1 infection
- Virologically suppressed (HIV-1 RNA < 50 c/mL for at least 6 months)
- Prescription for Juluca was issued independently from entering this study
- Ability to understand informed consent form and other relevant study documents

3.2.1.2 Exclusion Criteria

- Any contraindication according to Juluca SmPC
- Documented viral load > 50 c/ml at any timepoint within 6 months prior to inclusion into this study
- History of treatment failure

- Known or suspected substitutions associated with resistance to any NNRTI or INSTI
- Any antiretroviral therapy for the treatment of HIV-1 in addition to Juluca
- HBV-coinfection
- Current participation in the ongoing non-interventional study
- TRIUMPH (study number: 202033) or any interventional clinical trial irrespective of indication
- Previous participation in clinical trials involving Juluca

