3.2.2 Sampling

HIV-1-positive patients on a stable antiretroviral regimen for whom DTG/RPV is indicated according to the local SmPC may be selected for inclusion. The decision for prescription of the treatment regimen must be completely independent from study inclusion. However, patients eligible for inclusion, should be included with start of the new therapy regimen. Eligible patients must meet all inclusion and none of the exclusion criteria and must be thoroughly informed about all aspects of the study. The written informed consent must be obtained from the patient before any patient data is documented into the eCRF.

Investigators may enroll eligible subjects according to their availability and accessibility. The sample is deliberately non-stratified to reduce limitations on recruitment. This non-probabilistic convenience sampling may not ensure for the sample group to be a true representative of the population without sampling error.

Thus, this approach may result in some characteristics not being represented within the sample and limited diversity in terms of demographics and introduction of confounding factors, which may be considered in subgroup analysis

But as there are few further restrictions introduced by inclusion / exclusion criteria other than what is permitted under the local label, this study may provide evidence for a patient population that is broader than that of controlled clinical trials.

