6.5.5 Reporting of AEs and timelines

The study investigator involved is obliged to collect and report from the time of informed consent to study termination, all ADRs and SAEs.

All ADRs and SAEs will be reported to GSK global safety case management ([contact]) in the form of an electronic safety report within 24hrs of documentation via an automated process.

The safety-related information will be processed according to the legal requirements and country specific regulations to the competent authorities. The recording and reporting of safety data is in a pseudo anonymous format.

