## 7.4 Flow chart

For details see 11.2 and 11.3.

Forms	Visit	Enrollment visit	Baseline visit (=last visit before start of therapy with DTG+RPV)	(Routine-based) Follow-up visits until end of study	Study discontinuation	Independent of visits, continuous reporting
Informed consent		X				
In-, exclusion criteria		X				
Date of start with JULUCA			X			
Demography			X			
HIV/ART history			X			
Anamnesis (drug adherence, pregnancy, vital signs incl. weight)			X	X	X	
Laboratory parameters (hematology, metabolic parameters and clinical chemistry, transaminases and lipids)			X	X	X	
Comedication			X	X	X	
Comorbidities			X	X	X	
Referrals to another medical specialist			X	X	X	
Resistance mutation testing			X	X	X	
HIV TSQ			X	X	X	
HIV SDM			X	X	X	
Date & reason of study discontinuation					X	
Post ART					X	
ADR/SAE						X
HIV-related characteristics (laboratory parameters)						X

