## 10 Statistical Methods

### 10.1 Definition of analysis time window

### 10.2 Year 1, 2, and 3 follow-up windows

**Year 1 follow-up window** is defined as 9 to 15 months [275 days; 457 days] after the therapy start. This window applies to all variables incl. patient reported outcomes.

Rule for two or more assessments in the time window:

The closest available assessment to year 1 (365 days) after therapy start while the participant is on treatment and continued on study within the time window.

**Year 2 follow-up window** is defined as 21 to 27 months [640 days; 822 days] after the therapy start. This window applies to all variables incl. patient reported outcomes.

Rule for two or more assessments in the time window:

The closest available assessment to year 2 (730 days) after therapy start while the participant is on treatment and continued on study within the time window.

**Year 3 follow-up window** is defined as 33 to 39 months [1005 days; 1185 days] after the therapy start. This window applies to all variables incl. patient reported outcomes.

Rule for two or more assessments in the time window:

The closest available assessment to year 3 (1095 days) after therapy start while the participant is on treatment and continued on study within the time window.

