#### 10.2.1 Time period for incident (serious) adverse drug reactions and serious adverse events

For incident (S)ADRs/SAEs the following time window will be used:

Date of year 3 follow-up visit minus date of therapy start.

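### Inclusion at Juluca start is only a recommendation, so for any participant who consented later the eligibility look-back, the analysis clock and the safety-collection clock disagree, and the SAP has no check for it

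*Protocol*

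**What the plan says.** **Eligibility.** Protocol 3.2.1.2, repeated in SAP 7.3.2, excludes "Documented viral load > 50 c/ml at any timepoint within 6 months prior to inclusion into this study". The matching inclusion criterion, "Virologically suppressed (HIV-1 RNA < 50 c/mL for at least 6 months)", has no anchor date. The synopsis adds "Subjects must be on stable ART for at least 6 months prior to the inclusion into this study", again dated from inclusion. No listed criterion bars a patient already taking Juluca or limits the time since its start; the only related exclusion concerns other antiretrovirals taken alongside it.

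**Timing of entry.** Protocol 3.2.2 says: "However, patients eligible for inclusion, should be included with start of the new therapy regimen". This sentence is not in the criteria lists of Protocol 3.2.1 or SAP 7.3, gives no tolerance, and is not named among the deviations in SAP 9.

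**Analysis clock.** The SAP windows run from therapy start. For year 3 the value used is "The closest available assessment to year 3 (1095 days) after therapy start while the participant is on treatment and continued on study" within the window. The safety period in SAP 10.2.1 is "Date of year 3 follow-up visit minus date of therapy start".

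**Safety collection.** Protocol 6.5.5 requires reporting "from the time of informed consent to study termination, all ADRs and SAEs".

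**Visits.** The SAP 7.4 flow chart has an enrollment visit and, in a separate column, a "Baseline visit (=last visit before start of therapy with DTG+RPV)".

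**The concern.** The plan uses three starting points: study entry for the look-back, first dose for follow-up and exposure, and consent for event collection. They coincide only if consent and first dose fall together.

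Consider a patient who consents some months after starting Juluca. A viral load above 50 c/mL on Juluca in those months would have triggered the exclusion, and a patient who had already stopped for intolerance would be unlikely to be enrolled. Those who do enter have therefore been selected on their early on-drug outcome, yet their follow-up is counted from the first dose. The direction is known: suppression too high, rebound and ADR discontinuation too low.

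The interval from first dose to consent also counts as exposure although no ADRs or SAEs were being collected, which lowers the rates per patient-year. The dilution is greater if ADRs cluster soon after the switch.

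The plan's two rules are of unequal force. SAP 8.1 removes participants who violate a listed criterion from the mFAS, so an on-drug value above 50 c/mL before consent is a ground for removal. Late entry is not a named ground for anything.

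**Working it through.** **1. The plan's own figures.** At 90% efficacy, the smallest n giving a 95% Clopper–Pearson interval of width at most 0.10 is 158 (width 0.0997). Allowing for 30% dropout, 158 / 0.70 = 225.7, so 226. Both figures in Protocol 3.5 reproduce, and this point changes neither.

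**2. The clocks side by side.**

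| Item | Starts from | Source |
|---|---|---|
| Viral-load exclusion | Study inclusion, 6 months back | Protocol 3.2.1.2, SAP 7.3.2 |
| Stable ART | Study inclusion, 6 months back | Protocol synopsis |
| Year 1, 2, 3 windows | Therapy start | SAP 10.2 |
| SAE/ADR person-time | Therapy start | SAP 10.2.1 |
| SAE/ADR collection | Informed consent | Protocol 6.5.5 |
| Inclusion at therapy start | Recommended, no interval | Protocol 3.2.2 |

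**3. Possible effect on year-3 suppression.** Inputs:
- P = 0.90, the true success proportion, from Protocol 3.5.
- s, the share of starters reached late. Not in the documents; assumed.
- f, the share of eventual failures among them that show before entry. Not in the documents; assumed 10–50%.

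Entry removes s × f × (1 − P) of the starters, all failures, so

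observed success = P / (1 − s × f × (1 − P)).

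- s = 0 (3.2.2 followed): 0.90 / 1 = 90.0%. No bias.
- s = 0.25, f = 0.10: 0.90 / (1 − 0.0025) = 90.2%.
- s = 0.25, f = 0.50: 0.90 / (1 − 0.0125) = 91.1%.
- s = 1, f = 0.50 (extreme): 0.90 / 0.95 = 94.7%.

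In the third case failure reads 8.9% instead of 10%, so about one failure in nine is lost. The formula removes only eventual failures. A patient excluded for a transient value who would have been suppressed at year 3 pulls the other way.

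**4. Possible effect on SAE/ADR rates.** Inputs are N = 250 and the 30% maximum dropout over 3 years (Protocol 3.5), taken at constant hazard with exposure ending at dropout. The late share (10–40%) and the delay (0.25–0.5 years) are assumptions.

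- Hazard = −ln(0.70) / 3 = 0.1189 per year.
- Mean follow-up = 0.30 / 0.1189 = 2.52 years.
- Total = 250 × 2.52, about 631 person-years.
- Without event collection, low: 250 × 0.10 × 0.25 = 6.25 person-years, or 1.0%.
- Without event collection, high: 250 × 0.40 × 0.5 = 50 person-years, or 7.9%.

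With a constant event rate, the reported rate would be about 99% to 92% of the true rate. Because 30% is a maximum, 631 is a low total. With no dropout the total is 250 × 3 = 750, and the shares are 0.8% and 6.7%.

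**The case against.** The strongest reply is Protocol 3.2.2 itself. If sites followed it, inclusion and first dose coincide, the look-back covers the time before Juluca, and the bias is zero. The study is also described as prospective. Read strictly, the synopsis line on stable ART might keep out someone who changed regimen a few months before entry, although that line is not in the 3.2.1 lists and does not name the regimen. This reply stands: nothing in the documents shows that anyone entered late.

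Three stronger readings are tempting, and the documents do not support them.

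- A reader might infer that the plan does screen out early failures and that its results are biased. That drops the condition on late entry.
- A reader might take the separate enrollment and baseline columns in SAP 7.4 as provision for retrospective entry. The chart places consent before a pre-treatment baseline visit, so it is at most neutral.
- A reader might infer that questionnaire change is measured from an on-drug baseline. Under SAP 7.4 a form completed on Juluca is not a baseline form, and Protocol 4 analyses only complete pairs, so a late entrant should drop out of that comparison.

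Nor can the 30% dropout be used to count starters lost before enrolment. It is a study-dropout maximum, and someone never enrolled cannot drop out of the study. Above it serves only to estimate person-time.

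Finally, the lists in SAP 9 are open, and SAP 8.1 lets the data review meeting exclude participants with deviations, so late entry could be handled there. Nothing requires it, however, and SAP 10.4 reports only the first and last dates of enrolment and of therapy start, not each participant's interval.

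**Conclusion.** There is a gap in the plan, and its consequence is conditional. The timing rule that keeps the three clocks together is not enforceable as written, and the SAP neither measures departures from it nor protects the estimates against them. The safety period in SAP 10.2.1 would be wrong for any participant who consented after starting Juluca; that follows from the text alone.

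The size cannot be established from the documents. It is zero under full adherence to Protocol 3.2.2. On assumed inputs it is about 0.2 to 1.1 percentage points on suppression if a quarter entered late, and about 1–8% of person-time without event collection if 10–40% entered 3–6 months late. The 94.7% case requires every patient to be late and half of failures to fall before entry, and should not be read as an expectation. The sample size is unaffected.

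**What to change.** Rewriting the eligibility criteria would no longer change who was enrolled: sites were already enrolling by December 2018 (Amendment 1), and the SAP dates from July and August 2023. The useful changes are in the SAP:

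- **SAP 10.4:** tabulate days from therapy start to consent for all participants, including the number who consented after the first dose.
- **SAP 10.2.1:** start SAE/ADR person-time at the later of consent and therapy start, so that the denominator matches the collection period.
- **SAP 9 and 11.3:** list inclusion after therapy start, beyond a fixed tolerance set before the data are reviewed, as a protocol deviation. Repeat the primary, rebound and ADR-discontinuation analyses in participants who consented at or before therapy start plus that tolerance.
- **SAP 11.2.7:** state that a questionnaire counts as baseline only if completed before the first dose, in line with the flow chart.

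Consent and the Juluca start date both appear on the flow-chart forms, so no new data should be needed. The cost is some SAP wording, one interval table and a smaller n in the restricted analysis. If nobody entered late, the interval table settles the matter and the restricted analysis equals the main one.
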